2. OBJECTIVES AND ENDPOINTS

2.1 EFFICACY OBJECTIVES

2.1.1 Primary Efficacy Objective

The primary efficacy objective for this study is to evaluate the efficacy of prophylactic emicizumab (i.e., administered on a scheduled basis with the intent to prevent bleeds) compared with no prophylaxis in patients with hemophilia A without FVIII inhibitors on the basis of the following endpoint:

- The number of bleeds over time (i.e., bleed rate)

The endpoint will be analyzed separately for the two emicizumab arms: 1.5 mg/kg/week (wk) and 3 mg/kg/every 2 weeks (2wks). The primary endpoint is based on treated bleeds.

2.1.2 Secondary Efficacy Objectives

The secondary efficacy objectives for this study are as follows:

- To evaluate the efficacy of prophylactic emicizumab (in each individual emicizumab arm) on the basis of the following endpoint:

Change in the number of bleeds over time compared with the patient's historical bleed rate *

- To evaluate the efficacy of prophylactic emicizumab administered at 1.5 mg/kg/wk or 3 mg/kg/2wks subcutaneously compared with no prophylaxis for patients previously treated with episodic FVIII on the basis of the following endpoints:
 - All bleeds over time
 - Spontaneous bleeds over time (spontaneous bleed rate)
 - Joint bleeds over time
 - Target joint bleeds over time (target joints are defined as joints with ≥ 3 bleeds occurring in the same joint over the last 24 weeks prior to study entry)
 - HRQoL of patients according to Haem-A-QoL (aged ≥ 18) or Haemo-QoL-Short Form (aged 12–17) scores after 24 weeks
 - Health status of patients according to European Quality of Life 5-Dimensions-5 Levels Questionnaire (EQ-5D-5L) scores after 24 weeks
- To evaluate the efficacy of prophylactic emicizumab administered at 1.5 mg/kg/wk subcutaneously for patients previously treated with prophylactic FVIII on the basis of the following endpoint:
 - Maintaining adequate control of bleeding by evaluation of the bleed rate *

* Analyses will be performed for treated bleeds and all bleeds.

2.1.3 Exploratory Objectives

The exploratory objectives for this study are as follows:

- To assess satisfaction regarding treatment with emicizumab prophylaxis versus FVIII prophylaxis according to the Satisfaction Questionnaire–Intravenous Subcutaneous Hemophilia Injection (SQ-ISHI) in patients previously treated with prophylactic FVIII
- To assess treatment preference for emicizumab prophylaxis versus FVIII prophylaxis or episodic therapy according to the preference survey
- To assess changes in number of days away from school/work during treatment with prophylactic emicizumab compared with no prophylaxis
- To assess changes in number of hospitalization days during treatment with prophylactic emicizumab compared with no prophylaxis
- To assess potential PD biomarkers of emicizumab, including but not limited to aPTT, thrombin generation, and FVIII activity
- To assess potential serum and plasma biomarkers of bone and joint health
- To evaluate the effect of emicizumab prophylaxis treatment on activity compared with activity at baseline.
- To evaluate the effect of emicizumab prophylaxis treatment on activity compared with no prophylaxis

2.2 SAFETY OBJECTIVE

The safety objective for this study is to evaluate the overall safety of prophylactic emicizumab compared with no prophylaxis in patients with hemophilia A without inhibitors on the basis of the following endpoints:

- Incidence and severity of adverse events
- Incidence and severity of thromboembolic events
- Changes in physical examination findings and vital signs
- Incidence of laboratory abnormalities
- Incidence and severity of injection-site reactions
- Incidence of adverse events leading to drug discontinuation
- Incidence of severe hypersensitivity, anaphylaxis, or anaphylactoid reactions
- Incidence and severity of thrombotic microangiopathy
- Incidence and clinical significance of anti-emicizumab antibodies
- Incidence of de novo development of FVIII inhibitors in patients receiving emicizumab prophylaxis

2.3 PHARMACOKINETIC OBJECTIVE

The PK objective for this study is to characterize the exposure (trough plasma concentration) to emicizumab in patients treated on weekly or every 2 weeks dosing schedule at the following timepoints:

- Every week during Weeks 1–4 on emicizumab
- Every 2 weeks during Weeks 5–8 on emicizumab
- Every 4 weeks during Weeks 9–24 on emicizumab
- Every 8 weeks during Weeks 25–48 on emicizumab
- Every 12 weeks thereafter while on emicizumab, until the end of the study

3. STUDY DESIGN

3.1 DESCRIPTION OF STUDY

This randomized, multicenter, open-label, Phase III clinical study will enroll patients aged 12 years or older with severe hemophilia A (intrinsic FVIII level < 1%) without inhibitors against FVIII. Eighty-five patients who received episodic treatment with FVIII prior to study entry and experience at least 5 bleeds over the prior 24 weeks (ABR \geq 10) will be randomized in a 2:2:1 ratio (see [Figure 1](#)) to the following regimens:

- Emicizumab prophylaxis at 3 mg/kg/wk subcutaneously for 4 weeks, followed by 1.5 mg/kg/wk subcutaneously (Arm A),
- Emicizumab prophylaxis at 3 mg/kg/wk subcutaneously for 4 weeks, followed by 3 mg/kg/2wks subcutaneously (Arm B), or
- No prophylaxis control arm (Arm C).

Randomization will be stratified according to the number of bleeds patients experienced over the last 24 weeks prior to study entry—less than versus greater than or equal to 9 (or ABR 18)—to ensure a balance of patients with lower versus higher number of bleeds in all arms. All patients will use episodic treatment with FVIII at the lowest expected dose to achieve hemostasis in case of a breakthrough bleeding event (see below).

In addition, 40–60 patients with severe hemophilia A who received FVIII prophylaxis prior to study entry will be enrolled and will receive emicizumab prophylaxis at 3 mg/kg/wk subcutaneously for 4 weeks, followed by 1.5 mg/kg/wk subcutaneously (Arm D; see [Figure 1](#)). A minimum of 40 patients in this group will complete at least 24 weeks of observation in an ongoing non-interventional study (BH29768) prior to enrollment in this study. Eligibility for all patients in Arm D will be based on investigator's attestation of adequate prophylaxis regimen in the 24 weeks prior to study entry.

To avoid bleeds before adequate emicizumab plasma concentration is reached, these patients will continue their regular FVIII prophylaxis until the second emicizumab loading dose. At the end of the first week of treatment, 95% of patients are expected to achieve emicizumab level of 8 µg/mL, which is projected to have FVIII activity equivalent to approximately >2%. Thrombotic events were not found in the Japanese Phase I/II study where doses of FVIII were administered to treat breakthrough bleeds while patients had higher emicizumab steady-state level, supporting the safety of this approach. Importantly, routine prophylaxis will be prohibited for all patients enrolled in Arms A, B, or C and for patients in Arm D immediately after the second emicizumab dose.

Study enrollment will take place at the Week 1 visit. A patient who fulfills the inclusion and exclusion criteria should be enrolled and assigned to a treatment arm at the Week 1 visit, the same day when the first dose of emicizumab is due for patients in Arms A, B, and D.

[figure not shown]
Emicizumab is intended for prophylactic use only (i.e., not to treat bleeds that have already occurred). The primary efficacy analysis, defined as comparing the number of bleeds over time for patients randomized to receive prophylactic emicizumab versus no prophylaxis will be conducted at the earliest timepoint when all randomized patients (Arms A, B, or C) and a minimum of 40 patients from Arm D have either completed 24 weeks in the study or discontinued from the study. Therefore, there will be a range of observation periods from 6 to approximately 12 months, or longer. Study patients will be enrolled globally from the Americas, Europe, Africa, and Asia-Pacific region.

To obtain additional safety and efficacy data on emicizumab, patients who are randomized to the no prophylaxis arm (control arm, Arm C) will be expected to switch after 24 weeks to receive emicizumab prophylaxis at 3 mg/kg/2wks maintenance dose after 4 weeks of 3 mg/kg/wk loading dose. This dose was chosen to enhance the safety and efficacy data obtained with Arm B patients.

After completing at least 24 weeks of treatment with prophylactic emicizumab, patients who receive emicizumab prophylaxis (Arms A, B, D, or Arm C after treatment switch) and derive clinical benefit will be allowed to continue emicizumab until marketing authorization as part of this study or a separate extension study, as long as they continue to derive clinical benefit and emicizumab is still in clinical development (see Section 4.3.4). Those who are well controlled ($ABR < 4$) will continue treatment on their assigned emicizumab regimen; whereas, patients in Arms A, B, or C (after 24 weeks on emicizumab) who experience suboptimal control ($ABR \geq 4$) will be offered the option to escalate to 3 mg/kg/wk after approval from the Medical Monitor. Patients in Arm D who experience suboptimal control while on emicizumab prophylaxis at the maintenance dose, will have the opportunity to escalate to 3 mg/kg/wk immediately after the second qualifying bleed. Criteria and details of dose escalation are described in Section 4.3.2.

Figure 1 Study Schema

Phase III Non-Inhibitor - Design

2wks= every 2 weeks; 6moBR=6 months bleed rate; BR=bleed rate; FVIII=factor VIII; mo=month; R=randomization; wk=week.

^a All patients will receive loading with four weekly doses of emicizumab 3 mg/kg/wk prior to starting maintenance.

A 6 mg/kg every 4 weeks (4wks) maintenance dosing regimen is being evaluated in Phase III studies BH29992 and BO39182 in addition to the 1.5 mg/kg/wk and 3 mg/kg/2wks maintenance dosing regimens evaluated in this study. The observed

exposures (i.e., average concentration at steady state) of multiple doses of these three dosing regimens are comparable and lead to similar efficacy and safety profiles (see Section 3.3.1). Hence, 6 mg/kg/4wks will be offered as a permitted dosing regimen for patients who continue in this study during study prolongation.

Upon implementation of protocol Version 4, treatment duration will be extended until 5 years after the last patient is enrolled to enable the collection of additional safety and efficacy data. During this study prolongation, each patient may choose a preferred emicizumab dosing regimen among those permitted (i.e., emicizumab 1.5 mg/kg/wk, 3 mg/kg/2wks, or 6 mg/kg/4wks) and continue on that dosing regimen until discontinuation from the study. Instructions for switching the dosing regimen are outlined in Section 4.3.2.

During the study, individual bleeds will be captured as they occur, while HRQoL, health status, patient safety, patient preference and satisfaction, activity level, and days of school or work missed will be assessed as outlined in the schedule of assessments. Patients (or their caregiver) will be asked to record on an electronic, handheld device their bleeds (i.e., start date and time, reason, type, location, and associated symptoms of each bleed) and hemophilia-related medication use (i.e., start date and time, reason, type, dose of injection, and number of doses) at least weekly, when a bleed occurs, or when a hemophilia medication was taken at home or in the clinic.

Throughout the study, biomarkers related to thromboembolism (e.g., D-dimer, prothrombin 1.2 fragment) and emicizumab trough concentrations will be collected as per the schedule of assessments. Immunologic biomarkers (i.e., anti-emicizumab antibodies and anti-FVIII antibodies) will also be measured as per the schedule of assessments (see [Appendix 1](#)).

Exploratory PD biomarkers (e.g., aPTT, FVIII activity, thrombin generation assay) will be collected as per the schedule of assessments. As values for some of these tests are normalized by low plasma concentrations of emicizumab, a variety of assay formats (one stage, chromogenic) and modifications (predilution of patient plasma) will be investigated for assessment of PD response at higher emicizumab plasma concentrations. However, it is not expected that these biomarkers will be used to guide dosing or the selection of patients to be treated with emicizumab. Rather, these biomarkers may be used to identify a future assay for the monitoring of emicizumab activity.

Physical examinations, including Hemophilia Joint Health Score (HJHS; see [Appendix 8](#)), vital signs assessments, ECGs, and laboratory assessments will be collected as per the schedule of assessments and will be the same for all patients, with the exception that emicizumab PK and ADAs will not be measured in patients in Arm C prior to the switch to emicizumab treatment. Adverse events will be captured as they occur for the duration of the study.

All patients who receive emicizumab in the study will undergo PK assessments. A washout period from FVIII therapy is not required prior to inclusion because FVIII replacement does not interfere with emicizumab PK assessments, and some patients with hemophilia A require frequent dosing with FVIII to treat bleeds or for prophylaxis.

An independent Data Monitoring Committee (iDMC) composed of at minimum hemostasis/thrombosis experts and a statistician will be in place for the duration of the study and will monitor patient safety at pre-specified intervals and ad hoc as needed throughout the study (to be described in the iDMC charter).

Breakthrough bleeds for patients receiving emicizumab will be treated with FVIII at the lowest FVIII dose expected to achieve hemostasis and captured as they occur on the handheld device. Patients (or their caregiver) will report bleed information, including site of bleed, type of bleed, category of bleed, time of each individual bleed (day, start time), symptoms of bleed, and treatment for bleed. During the study patients will enter bleed and medication data at least weekly. Of note, the clinical experience in the ongoing Phase I and I/II clinical studies includes the treatment of breakthrough bleeds with FVIII or bypassing agents in patients receiving emicizumab (over 60 bleeds treated) without any related safety concerns reported. However, in the ongoing Phase III Study BH29884 (adolescent and adult patients with hemophilia A with FVIII inhibitors), 3 events of TMA and 2 thromboembolic events were observed in patients on emicizumab who concomitantly used repeated doses of aPCC for the treatment of breakthrough bleeds (see Sections 1.2, 1.3, 5.1.2.4, and 5.1.3). Although FVIII and aPCC are fundamentally different in their potential interaction with emicizumab, investigators should keep in mind that circulating emicizumab increases patients' coagulation potential. Therefore, it is recommended that:

- Breakthrough bleeds should be treated with the lowest FVIII dose expected to achieve hemostasis, which may be lower than the patients' prior FVIII dose. Investigators should review with patients the dose to be used to treat breakthrough bleeds.
- If breakthrough bleeding does not resolve after the first dose of FVIII, patients should be instructed to contact the treatment center before infusing multiple FVIII doses.
- Investigators and patients should consider objective verification of bleeds.

Investigators will contact the Medical Monitor in the event of suspected lack or loss of efficacy of emicizumab in order to discuss potential laboratory evaluations (e.g., anti-emicizumab antibodies, coagulation tests) to be performed as well as to re-evaluate their patient's benefit-risk of continued treatment.

The reason for the use of FVIII products will be documented (e.g., bleeding, one time prophylaxis, etc.). A thorough documentation of the treatments for bleeds will be required, including agent, start time, dose, route of administration, and number of infusions needed to treat the bleed.

A non-interventional study (BH29768) has been initiated to document the number and types of bleeds and current treatment with episodic or prophylactic FVIII agents, as well as to collect information on HRQoL, health status, and safety in patients with hemophilia A. The assessments in the non-interventional study will mitigate the risk of underreporting of bleeds that likely occurs in the real world, and the resulting data will serve as a source of comparator information for some analyses conducted in the Phase III clinical studies, including this study. In addition, the non-interventional study will enable earlier identification and confirmation of patients who may qualify for the Phase III clinical study. It is anticipated that a significant number of patients participating in Study BH29768 will enroll in this study, as long as they meet the inclusion and exclusion criteria and are able to enroll at a participating site while the study is open for enrollment.

Activity assessment will be conducted at all sites participating in this study, and all patients screened and enrolled will be expected to participate. Participation will not be mandatory and will not impact participation in Study BH30071. Patients will be asked to wear the study device for 2 weeks during Weeks 1–2, 23–24, and 47–48. Patients will return their study devices to the respective site at Weeks 3, 25, and 49 and each site will transfer the data from the device to the database. These data will be analyzed to generate the daily step count (DSC) values for each patient.

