5.3.1 Adverse Event Reporting Period

Investigators will seek information on adverse events at each patient contact. All adverse events, whether reported by the patient or noted by study personnel, will be recorded in the patient's medical record and on the Adverse Event eCRF.

After informed consent has been obtained but prior to randomization (randomized arms) or initiation of study drug (non-randomized arm), only serious adverse events caused by a protocol-mandated intervention (e.g., invasive procedures such as biopsies, discontinuation of medications) should be reported (see Section 5.4.2 for instructions for reporting serious adverse events).

After randomization (randomized arms) or initiation of study drug (non-randomized arm), all adverse events will be reported until the patient completes his or her last study visit (i.e., 24 weeks after the last dose of study drug). After this period, the investigator should report any serious adverse events that are believed to be related to prior study drug treatment (see Section 5.6).

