Appendix 1 Schedule of Assessments

Schedule of Assessments—Arms A, B, and D																			
	Screen- ing	Wk 1	Wk 2	Wk 3	Wk 4	Wk 5	Wk 7	Wk 9	Wk 13	Wk 17	Wk 21	Wk 25	Every 8 Wks from Wk 33	Wk 49	Every 12 Wks from Wk 61	Every 24 Wks from Wk 73	Daily/ weekly ^a	Study Com- pletion/ ET	Safety F/U Visit ^b
Informed consent ^c	x																		
Inclusion/exclusion criteria	x																		
Medical history and demographics ^d	x																		
Physical examination (including weight) ^e	x	x				x						x		x	x	x		x	x
Height	x											x		x					
Vital signs (including weight) ^f	x	x ^f	x	x	x	x	x	x	x	x	x	x ^f	x	x ^f	x	x		x ^f	x
HJHS ^g	x													x					
Serum pregnancy test ^h	x	x																	
Concomitant medications ⁱ	x	x				x		x	x	x	x	x	x	x	x	x		x	x
ECG ^j	x	x ^j				x						x						x	
Safety laboratory assessments ^h	x ^h	x	x	x	x	x	x	x	x	x	x	x	x	x	x	x		x	x
Anti-FVIII antibodies ^k	x ^k	x		x					x			x	x	x	x	x		x	x
Anti-emicizumab antibodies ^l		x ^l				x		x ^l	x	x ^l	x	x ^l	x ^l	x ^l	x ^l	x ^l		x	x ^l
Bleed/medication questionnaire ^m																	x		
Bleed/medication data review ⁿ		x				x		x	x	x	x	x	x	x	x	x		x	x

RO5534262—F. Hoffmann-La Roche Ltd
110/Protocol BH30071, Version 4

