Appendix 1 Schedule of Assessments (cont.)

Schedule of Assessments—Arm C (Screening to Switch to Emicizumab)								
	Screen- ing	Wk 1	Wk 5	Wk 9	Wk 13	Wk 17	Wk 21	Daily/ weekly ^a
Informed consent ^c	x							
Inclusion/exclusion criteria	x							
Medical history and demographics ^d	x							
Physical examination (including weight) ^e	x	x						
Vital signs (including weight) ^f	x	x ^f	x	x	x	x	x	
Height	x							
Serum pregnancy test ^h	x							
HJHS ^g	x							
Concomitant medications ⁱ	x	x	x	x	x	x	x	
ECG ^j	x	x ^j						
Safety laboratory assessments ^h	x ^h	x						
Anti-FVIII antibodies ^k	x							
Bleed/injection questionnaire ^m								x
Bleed/injection data review ⁿ		x	x	x	x	x	x	
Adverse events ^o		x	x	x	x	x	x	
HRQoL and health status ^q		x			x			
Activity measure (optional) ^u		x						
PD biomarkers assessment ^s		x						
Bone biomarkers (fasted) ^t		x						
RCR blood DNA sample (optional) ^w			x					

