##### **4.7.2 Adverse Events**

Adverse events will be summarized and presented by System Organ Class mapped term, appropriate thesaurus level, and toxicity grade (WHO Criteria) for each treatment arm. All adverse events will be coded using the current version of MedDRA at time of database closure. The total number and percentage of patients with at least one adverse event and total number of adverse events will be summarized. Separate

adverse event summaries for serious adverse events, adverse events of special interest, severity, relatedness, and discontinuation/modification will be provided.

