#### **4.7.3 Laboratory Data**

For clinical laboratory data that were collected from local laboratories, summary statistics in International System of Units (SI) will be presented by treatment arm. Laboratory data not collected in SI units will be converted to SI units as applicable. In addition, shift tables describing changes from baseline will be presented using the WHO toxicity grading scale.

Data on the impact of immunogenicity (anti-emicizumab antibodies) on safety, efficacy, and/or clinical pharmacology and pharmacokinetics will be summarized using standard language/terminology ([Shankar et al. 2014](#)).

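### Protocol 3.1 says laboratory assessments are the same in all arms, but the schedule and the switch-date rule leave Arm C's control period with no scheduled post-baseline safety laboratory value, so the planned laboratory comparison with no prophylaxis is either biased against emicizumab or has almost no control data

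*Protocol*

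**What the plan says.** Protocol 3.1 covers physical examinations, vital signs, ECGs and laboratory tests in one sentence. It says that "laboratory assessments will be collected as per the schedule of assessments and will be the same for all patients". One exception is named: before the switch, Arm C has no PK or anti-drug antibody sampling. Safety laboratory tests are not excepted.

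Appendix 1 has separate tables. The one headed "Schedule of Assessments—Arms A, B, and D" marks safety laboratory assessments at Weeks 2, 3, 4, 5, 7, 9, 13, 17 and 21. The one headed "Schedule of Assessments—Arm C (Screening to Switch to Emicizumab" marks them at Screening and Week 1 only. Arm C's next panel is at Week 25, the switch visit, drawn before the first dose. SAP Appendix 2 repeats this schedule.

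A comparison is planned. The safety objective in Protocol 2.2 is emicizumab against no prophylaxis, and incidence of laboratory abnormalities is one of its endpoints. SAP 4.1 says the randomized efficacy comparisons will have a corresponding safety analysis. SAP 4.7.3 presents laboratory data by treatment arm and adds that "shift tables describing changes from baseline will be presented using the WHO toxicity grading scale". The randomized safety set SAF1ND (SAP 4.2.5) admits any Arm C patient with a Week 1 visit and does not require a post-baseline laboratory value. Protocol 6.6 splits Arm C at the switch: data up to the day before count as control, and data on or after that date are reported separately.

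For adverse events, Protocol 3.1 says "Adverse events will be captured as they occur for the duration of the study", and Protocol 5.3.1 says "Investigators will seek information on adverse events at each patient contact". SAP 4.7.2 says "The total number and percentage of patients with at least one adverse event and total number of adverse events will be summarized".

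**The concern.** A count of patients with an abnormality depends on how often they are tested. If one arm is tested nine times and the other not at all, the tested arm can only look worse or equal on any incidence measure, whatever the drug does. Someone who relies on the sentence in 3.1 would not expect this, because it says testing is alike.

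One endpoint of the comparative safety objective is at stake. As written, the laboratory part has no fair comparator, and neither document mentions the unequal testing or adjusts for it. The primary efficacy analysis is not affected.

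**Working it through.** **The plan's own safety figure.** The only numerical safety statement (Protocol 6.1, SAP 2.4) is a probability of 0.66–0.72 of seeing an event of 1% incidence among 108–128 emicizumab patients. It reproduces: 1 − 0.99^108 = 0.662 and 1 − 0.99^128 = 0.724. It is not in dispute, and it does not address the comparison with Arm C.

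**Scheduled visits, Weeks 2–21 (Protocol Appendix 1).**

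| Assessment | Arms A/B | Arm C |
|---|---|---|
| Safety laboratory | 9 | 0 |
| Adverse-event visit | 9 | 5 (Weeks 5, 9, 13, 17, 21) |
| ECG | 1 | 0 |
| Physical examination | 1 | 0 |
| Anti-FVIII antibodies | 2 | 0 |

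None of the laboratory, ECG or examination differences is covered by the PK and antibody exception in 3.1.

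**Week 25.** Arm C's panel falls on the switch date. Under Protocol 6.6, data on that date are outside the control summaries. For a patient who switches at Week 25, scheduled post-baseline panels in the control period therefore number 0. Only unscheduled tests remain.

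**What the tables would then show.** There are two cases.

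1. The denominator is all of SAF1ND. A control with no post-baseline test counts as having no abnormality, so the table is biased against emicizumab.
2. A post-baseline value is required, as a shift table normally needs. The control column is then essentially empty, and there is no comparison.

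**Illustration of case 1 with no drug effect.** The inputs are k = 9 draws against 0, and 68 emicizumab patients (34 + 34, Protocol 6.1). The per-draw chance p of an abnormal panel and the within-patient correlation ρ are assumptions, because the documents give neither.

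- Independent draws: P(at least one) = 1 − (1 − p)^9.
- Correlated draws (beta-binomial): P(at least one) = 1 − ∏ (b + i)/(a + b + i) for i = 0 to 8, where a = p(1 − ρ)/ρ and b = (1 − p)(1 − ρ)/ρ. Example: p = 5% and ρ = 0.5 give a = 0.05, b = 0.95 and 13.4%.

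| p | ρ = 0 | ρ = 0.2 | ρ = 0.5 | ρ = 0.8 | Control |
|---|---|---|---|---|---|
| 0.5% | 4.4% | 2.5% | 1.4% | 0.8% | 0% |
| 1% | 8.6% | 5.0% | 2.8% | 1.6% | 0% |
| 2% | 16.6% | 9.7% | 5.5% | 3.2% | 0% |
| 5% | 37.0% | 22.8% | 13.4% | 7.8% | 0% |

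At p = 1%, the expected number of flagged emicizumab patients runs from 68 × 0.0159 = 1.1 (ρ = 0.8) to 68 × 0.0865 = 5.9 (ρ = 0). At p = 5% it runs from 5.3 to 25.1. The control figure is zero by construction, not by observation: with nine independent draws at p = 1%, the 17 controls would be expected to give 17 × 0.0865 = 1.5 such patients.

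The table covers Weeks 2–21 only. Arms A and B continue laboratory visits from Week 25 to the clinical cutoff, and neither Protocol 6.6 nor SAP 4.7.3 limits the tables to the first 24 weeks, so unrestricted tables would be more unequal.

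**The case against.** The strongest reply has four parts.

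- **The schedule governs.** The sentence in 3.1 itself defers to the schedule of assessments, so sites are not misdirected. This stands, and the harm lies in the analysis and its reading.
- **The extra visits follow from treatment.** Protocol 4.3.2 requires the first five administrations in a monitored setting. Safety is summarized descriptively with no test, and any bias runs against emicizumab, so harm would not be hidden. All of this stands and limits the severity. It does not supply the missing control data.
- **An excess is not certain.** A reader might infer that the tables will show more abnormalities on emicizumab through ascertainment alone. The documents do not support that. SAP 4.7.3 plans summary statistics and shift tables. If these require a post-baseline value, the result is a missing comparison and not an excess. A reader might also credit the Week 25 panel to control and count 10 draws against 1, which gives 9.6% against 1% at p = 1% and 40% against 5% at p = 5%. That assumes independent draws and conflicts with Protocol 6.6. At ρ = 0.5 the 40% falls to 14%.
- **Adverse events are captured continuously.** A reader might infer an adverse-event excess from 9 visits against 5. Capture is ongoing in every arm, and the sample question in Protocol 5.3.2 asks about the time since the last visit, so Arm C's Week 5 visit covers Weeks 1–4. A laboratory value becomes an adverse event only under the conditions in Protocol 5.3.5.5. Fewer contacts may lower the recall of minor events, but nothing in the documents shows that they do.

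**Conclusion.** The contradiction is exact. Protocol 3.1 says laboratory assessments are the same apart from PK and antibodies, while Appendix 1 gives nine scheduled safety-laboratory visits against none in Weeks 2–21. Read with the switch-date rule in 6.6, the control period has no scheduled post-baseline laboratory value for a patient who switches at Week 25. The comparison of laboratory abnormalities and shifts with no prophylaxis is therefore either biased against emicizumab or has an essentially empty control column.

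Which of the two applies depends on a denominator the SAP does not state. The size of any bias depends on a background rate and a within-patient correlation the documents do not give, so the percentages above are illustrations only. Under-ascertainment of adverse events in Arm C is possible and unproven. The point deserves correction because it affects a stated safety endpoint and is cheap to repair. It does not touch the primary result.

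**What to change.** 1. Protocol 3.1: reword the sentence so that it matches Appendix 1 and names the laboratory, ECG, examination and anti-FVIII differences before the switch.
2. Protocol 6.6 and SAP 4.7.3: state that the Arm C sample drawn before the first dose at Week 25 belongs to the control period. Without this, step 3 has no control data.
3. SAP 4.7.3: restrict between-arm laboratory comparisons to the change from baseline to that shared Week 25 visit.
4. SAP 4.7.3: present worst-post-baseline and any-abnormality tables for the emicizumab arms without a comparative control column, or with a note that control had no scheduled draws. State the denominator.
5. Optional: split the Arms A/B versus C adverse-event table at Week 4. The extra visits in Weeks 2–4 then fall in the first part, and Week 7 is the only unmatched visit in the rest through Week 21.

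The cost is two short protocol edits and revised table specifications, with no new visits or samples. The downside is fewer data points in the comparative laboratory table, and under step 4 the frequency of any abnormality is no longer compared between arms.
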